## Eligibility Criteria for Participants

***Inclusion criteria:*** 1) Able to speak, read, and write in English or Spanish, 2) Aged  $\geq 18$  years; 3) Willing to provide a valid form of identification for verification; 4) Willing to participate in any assigned arm of the intervention; 5) Having been diagnosed with HIV  $\geq 6$  months ago; 6) Have an HIV-1 RNA level  $>50$  copies/mL, or at least one “no-show” visit in the past 12 months, or report either not virally suppressed in the past 12 months or virally unsuppressed in the past 12 months; 7) Own a smartphone; 8) Ability and willingness to provide informed consent for study participation and consent for access to medical records; and 9) Live in the United States.

***Participants are not eligible if they meet any exclusion criteria:*** 1) Reside in a nursing home, prison, and/or receiving in-patient psychiatric care at time of enrollment; 2) Terminal illness with life expectancy  $<3$  months; and 3) Planning to move out of the country in the next 3 months.

***Inclusion consideration:*** We carefully considered including newly diagnosed patients (diagnosed  $<6$  months) and have chosen to not include this subset of PLWH because: 1) Our piloted interventions did not include newly-diagnosed persons; 2) Newly-diagnosed individuals are treatment naïve and their adherence behaviors are unknown and may change frequently as they begin their ART regimen; and 3) The advent of rapid-start ART for newly-diagnosed individuals is currently under trial, providing an ART-initiation intervention for these individuals that could compromise our study results.

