## STATISTICAL PROCEDURES

### Sample Size and Power Calculation

Since this is a pilot study, we will be collecting a sample size to estimate the effect size for future efficacy trials and to establish the feasibility of this intervention.

*Sampling approach to successfully enroll PLWH who are not optimally engaged in HIV Care:* Using active and passive recruitment methods, the project coordinator will oversee and participate in recruitment efforts. The study staff hired through this project and the peer-to-peer networking efforts will be used to recruit study participants. Our study team has extensive experience in recruitment efforts for projects similar to the one proposed here and will be able to successfully recruit the study sample.

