### Eligibility Screening

Potential participants will either call, text, or email the study team via the advertised phone number or email address. Screening will be conducted over the phone or electronically via REDCap. Each potential participant will be screened for eligibility based on the inclusion/exclusion criteria. Participants who do not have a recent ( $\leq 8$  weeks) available viral load test result will need to complete a study DBS (dried blood spot) collection as part of a screening visit. Participants may also sign a Release of Information (ROI) form to allow study staff to access their electronic medical record (EMR) and determine eligibility based on past viral load data and "no-show" visits. Forms completed electronically will be conducted via video conferencing such as Skype, Zoom, or FaceTime using REDCap to collect the e-ROI and answer participant questions. Through the REDCap platform, participants will be able to securely download a copy of the e-ROI for their records. As part of the REDCap e-consent platform e-ROIs will be automatically archived and securely stored in REDCap. If deemed eligible, staff will work with the potential participant to schedule an enrollment visit at a convenient time for the participant.

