### Study Outcomes

The study outcomes are described in Table 4. The primary outcome of the study is viral suppression which will be operationalized as viral load  $\leq 50$  at 3 months. Viral load is the biologic correlate of the ART adherence behavior; yet, to achieve biologic change, there must be change in the adherence behavior. As suggested through the "Undetectable equals Untransmittable," or "U=U," public health campaign, PLWH who take ART as prescribed and achieve and maintain viral suppression have effectively no risk of sexually transmitting the virus to a serodiscordant partner. Our secondary and related outcomes include ART adherence measured in two ways: 1) a single-item self-report measure, an empirically validated instrument, and 2) electronic pill bottle data, collected via the CleverCap bottle. The electronic

pill bottle data provide a less subjective measure as compared to self-report. We will also measure missed healthcare visits using electronic medical record (EMR) data.

Limitations and Considerations of the Study Outcome. We recognize that all the approaches for measuring viral suppression and ART adherence are limited. First, viral suppression does not directly measure a behavioral outcome but, rather, the biologic effects of the behavior. Second, the self-report measure is biased

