**Table 4. Measures and Schedule of Events**

	Screening	Baseline	3 mos
Sociodemographic:(e.g., age, race/ethnicity, education, housing)		X	
Primary Outcome Measures			
Viral Load through dried blood spot kit	X		X
Secondary Outcome Measures			
ART adherence (SRSI)  and the CleverCap (intervention group only)	X		X
Additional Outcome Measures			
Quality of Life (PROMIS-29) 		X	X
HIV Symptom Index 		X	X
Engagement in HIV Care 		X	X
Mediators			
The HIV Medication Taking Self-Efficacy Scale		X	X
Motivation and outcome expectancies of ART adherence are assessed as three separate dimensions: attitudes, norms, and behavioral intentions to adhere to ART medication 		X	X
Self-regulation skills, which include self-monitoring, goal-setting, and enlistment of self-incentives/plans 		X	X
HIV-regulated Stigma 		X	X
Moderators			
Alcohol, Smoking & Substance Involvement Screening Test (ASSIST) 		X	X
Depression and Anxiety (Beck Symptom Inventory) 		X	X

and has ceiling effects. Finally, the electronic pill box is limited to data collected from the intervention group. While this is a limitation, providing the electronic pillbox to the standard of care (control group) is likely to bias our intervention effects since this pillbox will, in fact, have intervention effects as we have found from our preliminary findings from our WiseApp trial. We closely considered each of these limitations and have, therefore, decided that this three-pronged (i.e., viral load, self-report, and electronic pillbox) approach which will provide the most rigorous approach to measuring our primary and secondary outcomes of viral suppression and ART adherence.

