## **Data Analysis**

The distribution of all variables will be assessed, as will the correlations between all variables and the primary/secondary outcomes. We will assess for patterns of missing data, which are expected to be low as the study utilizes computer-assisted self-interview (CASI) for sensitive data, which reduces participant nonresponse. The primary anticipated reason for missing data is attrition due to loss to follow-up. Based on our preliminary studies, we are accounting for 20% attrition from randomization to the 3-month assessment.

All multivariate analyses will be preceded by standard descriptive bivariate analyses to describe key variables and relationships among them. These analyses will include means, frequency tables, histograms, and examination of distributions. All statistical tests will be two-sided tests with the level of significance at 0.05. The primary hypothesis 1 will be a comparison of viral suppression (primary outcome) between CHAMPS Pilot and standard of care. We will also compare the drop in viral load (measured in logarithmic scale with base 10) between the two groups. Our secondary and related outcome is ART adherence measured in two ways: 1) a single-item self-report measure, an empirically validated instrument (SRSI) and 2) electronic pill bottle data which we will be collecting in the intervention group since all participants will receive a CleverCap bottle for their medications. All the analyses will be based on initial assignment to groups, using the intention-to-treat principle.

The primary hypothesis 1 ( $H_1$ ) will be tested using a generalized linear mixed model (GLMM) with logit-link function for binary outcomes (i.e., viral suppression) or a linear mixed model (LMM) for continuous outcomes (i.e., viral load measured in logarithmic scale) to account for the non-independence of repeated measurements within individuals. The models will include a random intercept and fixed effects for intervention group, time, and interaction term of group and time which is for testing efficacy of the intervention. The model may include

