### Human Subjects Involvement, Characteristics, and Design

#### Characteristics of the Population:

The trial will involve the recruitment and retention of men and women ( $n=40$ ) with HIV infection who are virally unsuppressed in the United States. Study volunteers must meet general criteria to be eligible for further screening for participation in the study. In most cases, this information will be acquired during a telephone interview prior to a screening/consent remote visit. *The inclusion and exclusion criteria have been carefully*

*selected to enroll the most appropriate study population while also ensuring the generalizability of the findings.* All participants will engage in a 3-month randomized adaptive intervention. The total study duration will be 3 months. A maximum of 25 follow-up interviews will be conducted, with an oversampling of participants in the intervention group.

Potential participants will be recruited online using social media platforms. Persons living with HIV (PLWH) will be included if they meet the following eligibility criteria:

There are limited inclusion criteria in order to support the generalizability of our findings.

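### The efficacy test for viral suppression is a group-by-time interaction, which is not the stated 3-month comparison and breaks down if few participants are suppressed at entry

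*Combined protocol and SAP*

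**What the plan says.** Study Outcomes gives the endpoint: "The primary outcome of the study is viral suppression which will be operationalized as viral load" of 50 or less at 3 months. Data Analysis gives the hypothesis: "The primary hypothesis 1 will be a comparison of viral suppression (primary outcome) between CHAMPS Pilot and standard of care". The next sentence adds a comparison of the fall in log10 viral load, so change wording is reserved for the continuous measure.

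The test for hypothesis 1 is then a generalized linear mixed model with logit link and random intercept for suppression, or a linear mixed model for log10 viral load. Both have "fixed effects for intervention group, time, and interaction term of group and time which is for testing efficacy of the intervention". Table 4 schedules "Viral Load through dried blood spot kit" at screening and 3 months only. No other between-arm test of suppression is named; the non-inferiority test later in Data Analysis compares month 3 with baseline.

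On who is suppressed at entry, the sections differ:

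- Characteristics of the Population describes people "with HIV infection who are virally unsuppressed in the United States".
- Eligibility Criteria for Participants also admits those with a missed visit, or who "report either not virally suppressed in the past 12 months or virally unsuppressed in the past 12 months". The inclusion list in the human-subjects section keeps the 12-month report but omits the missed-visit route.
- Eligibility Screening lets staff "determine eligibility based on past viral load data" and missed visits.

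On purpose, Sample Size and Power Calculation says "we will be collecting a sample size to estimate the effect size for future efficacy trials".

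**The concern.** The endpoint and hypothesis concern one contrast at one time point. The test treats entry suppression as a second outcome and asks whether the change in log-odds differs between arms. It therefore spends precision estimating a baseline group difference that randomisation already makes zero in expectation. When entry suppression is rare, the baseline cells are sparse or empty and the interaction becomes unstable or undefined.

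Low power is not the complaint, because the plan claims none. What is at stake is the quantity the pilot hands on. The interaction is a ratio of subject-specific odds ratios, and it is infinite whenever exactly one arm has nobody suppressed at entry. A later trial would be sized on the 3-month difference in proportions. The plan gives no fallback for empty cells.

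**Working it through.** **Inputs from the document.** 40 participants (Design Overview), 1:1 (Randomization), so 20 per arm. Attrition is 20% (Data Analysis), so about 16 per arm at 3 months. Tests are two-sided at 0.05. The plan states no power or effect size, so there is no figure of its own to reproduce.

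**Assumed, not in the document.** The share suppressed at entry, q, and the 3-month suppression rates.

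**Step 1: what the term estimates.** Write the log-odds of suppression as b0 + u + bG·group + bT·time + bGT·group·time. The subject-specific 3-month log odds ratio is bG + bGT; the plan tests bGT alone. If q = 0 in both arms, the fit sends b0 to minus infinity and bT to plus infinity with a finite sum. Then bG absorbs the whole 3-month difference. Adding bGT improves nothing, so the likelihood-ratio statistic is 0.

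**Step 2: the same 3-month data, different entry status.** Fix the result at 11/16 v 5/16 suppressed, with 4 per arm missing, and assume anyone suppressed at entry stays so. Maximum likelihood by 41-point quadrature gives:

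| Suppressed at entry | LR p for interaction | Estimate |
|---|---|---|
| Nobody | 1.0 | not identified |
| 1 intervention | 0.69 | toward minus infinity |
| 1 control | 0.03 | toward plus infinity |
| 1 in each arm | 0.18 | finite |

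Replacing the first row's outcome with 14/16 v 2/16 still gives LR = 0. One person's screening status moves p from 0.69 to 0.03 and reverses the sign. Capping the random-intercept SD at 1.5 or higher leaves the two one-person cases at 0.62–0.69 and 0.03–0.05.

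**Step 3: chance of an empty arm at entry.** P = 1 − (1 − (1 − q)^20)². At q = 5%: 0.95^20 = 0.358, so P = 1 − 0.642² = 59%. At 10%: 0.9^20 = 0.122, so P = 23%. At 20% it is 2%, and at 30% it is 0.2%.

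**Step 4: large-sample precision.** Take 30% v 60% at 3 months, with occasions treated as independent. Variance of the 3-month log odds ratio = 1/(16·0.3·0.7) + 1/(16·0.6·0.4) = 0.298 + 0.260 = 0.558, so SE = 0.75. The interaction adds 2/(20·q·(1 − q)). At q = 10% that is 1.111, giving SE = √1.669 = 1.29 and a variance ratio of 3.0. The ratio is 4.8 at 5%, 2.0 at 25% and 1.7 at 50%.

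**Step 5: simulated rejection rates.** 30% v 70% at 3 months, 20 per arm, 20% random loss.

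- Model A: those rates apply to people unsuppressed at entry, and 90% of the entry-suppressed stay suppressed in both arms.
- Model B: those rates apply overall, with latent correlation 0.5 with entry status.

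The comparator is Firth logistic regression at 3 months on arm and entry suppression (yes/no).

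| q | A: interaction | A: 3-month | B: interaction | B: 3-month |
|---|---|---|---|---|
| 0% | 0% | 63% | 0% | 64% |
| 5% | 23% | 60% | 27% | 64% |
| 10% | 29% | 57% | 35% | 65% |
| 20% | 35% | 50% | 45% | 66% |
| 30% | 36% | 42% | 52% | 66% |
| 50% | 27% | 27% | 55% | 67% |

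The interaction column used 800 replicates per cell (Monte Carlo SE up to 1.8 points), the 3-month column 2,000 (up to 1.1). Separately coded repeats showed the same pattern; their Model A interaction figures were 26–30% at q = 5% and 31–39% at 10%. Under the null (Model A, q from 5% to 50%) the interaction rejected 5.0–6.6% and Firth 4.0–4.7%, so the gap is not bought by a liberal test.

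**Step 6: a direct estimate stays finite.** 11/16 − 5/16 = 37.5 percentage points, Newcombe 95% CI 3 to 62.

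**The case against.** - **The interaction is a conventional and unbiased choice.** Under randomisation bG is zero in expectation, so both contrasts share a null, and the interaction targets the subject-specific 3-month log odds ratio. This stands: the fault is precision, scale and fragility, not bias. It does not rescue a term that is unidentified or infinite.
- **Hypothesis 1 also has a linear mixed model for log10 viral load.** True. That model has no separation problem and matches its own stated target, so it is outside this criticism. It does not analyse the 50-copy endpoint.
- **Descriptive frequency tables will show the 3-month proportions anyway.** Probably, but a table is neither the named test nor a risk difference with an interval.
- **The worst case rests on one narrative phrase.** The eligibility criteria could admit many currently suppressed people. Extending Model A to 65% and 80% suppressed at entry shows no loss (18% v 17%, and 12–15% v 12%). This is the strongest point and it limits the size of the finding. The rate is unknown, however, and a primary test should not depend on it.
- **It is a 40-person feasibility pilot.** That bears on power, not on whether the effect size it sets out to estimate can be obtained.

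**Conclusion.** The concern holds and should be fixed. The mismatch between the 3-month endpoint and the interaction test is on the page and needs no assumption. The consequence depends on the share suppressed at entry, which the document does not give. At 0% the primary test fails completely; this is exact. At 5–10% an empty arm is likely or common (59% and 23%, exact given q), and the simulated power loss is about 28 to 37 points. At 20–30% the loss is 6 to 21 points, and at 50% it is between none and 12. The power figures rest on the assumed 30% v 70% rates and the two assumed links between entry and 3-month status. In these simulations the adjusted 3-month comparison was at least as powerful throughout the 0–50% range.

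**What to change.** In Data Analysis, make the primary analysis of hypothesis 1 the between-arm comparison of the proportion with viral load of 50 or less at 3 months, as randomised and adjusted for screening viral load. Firth logistic regression on arm and screening viral load (log10, or 50 or less v above 50) is one option; only the yes/no covariate was simulated here. An exact mid-p test stratified by screening suppression is another. Report the risk difference with a 95% confidence interval as the effect size, and say whether it is standardised from the model or unadjusted.

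Also state which screening value is used, since Eligibility Screening allows either the dried blood spot or a result from the previous 8 weeks. Reconcile the population descriptions in Eligibility Criteria for Participants, Characteristics of the Population and the human-subjects inclusion list, and report the share suppressed at entry by arm.

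The cost is SAP wording only. Both viral loads are already collected, and no participant, visit or assay is added. The model-based analysis conditions on arm and screening viral load when 3-month values are missing; an unadjusted complete-case interval does not, and should be labelled as such.

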### Design Overview

A pilot study will be conducted with 40 PLWH over 3 months. Participants will be randomly assigned to CHAMPS Pilot (intervention) or a standard-of-care control arm.

**Intervention Arm:** The CHAMPS Pilot intervention, outlined in Table 1, is a 3-month intervention guided by BA2C. The CHW will be demographically-matched to our study participant.

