### Procedures

All study visits will occur remotely via Zoom. Staff members will collect digital informed consent prior to enrolling into the study trial (See Protection of Human Subjects). The informed consent form provides details of the study procedures, risks, benefits, site contact information, and the nature of confidentiality and voluntary participation. The consent process also covers information on the study and compensation for time.

Participants in both the intervention and control arms will complete remote visits at the baseline and 3-month follow-up. Following the completion of the baseline study instruments, study participants in the CHAMPS Pilot intervention arm will be mailed a CleverCap™ Lite dispenser and trained on how to use it; they will also be trained by study team members on how to use the different features of the Wise App and receive medication reminders. Upon assignment to the intervention arm, a CHW is assigned to and meets with the participant as soon as possible, generally on the same day but no more than five business days. The CHW will deliver the interventions outline in Table 3 remotely throughout the course of the study. Participants will also be provided the opportunity to complete a follow-up interview at their follow-up visit. Follow-up interviews will be recorded via Zoom and will be semi-structured. Study staff members will take field notes and interview recordings will be transcribed prior to analysis.

Dried Blood Spot (DBS) kits will be used to measure participant viral load. DBS kits will be shipped to participants, allowing them to collect their sample in their home or other secure environment. Instructions will be included with the kit, including information about how to collect the dried blood spot and how to mail the sample back to the research team. Participants will be instructed to call research staff to confirm they have

received the kit, have collected the sample, and have mailed the sample back, as well as if they have any questions.

Participants will be texted appointment reminders for study visits. Hard to reach participants will also be sent scheduling reminders. These reminders will be sent via Qualtrics, REDCap and/or encrypted e-mails from the study's secure CUMC e-mail address.

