### Overview of Data Collection Time Points

Follow-up visits will be scheduled 30 days before to 30 days after the target window based on participant availability and site capacity. Timing of follow-up visits is scheduled to allow site flexibility while still scheduling follow-up visits within a reasonable time span.

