stratification variables, age, and sex as covariates. A site by group interaction will be also examined and included in each model (above) if significant at the .05 level. All analyses will be tested for goodness-of-fit using the Wald-type test, which shows satisfactory performance for models with fewer (<5) covariates. A similar GLMM will be used to test sustainability of the intervention at month 3. For this analysis, we will conduct a non-inferiority test to compare viral suppression rate between month 3 and baseline. For primary hypothesis 2 ( $H_2$ ), testing for intervention effect on ART adherence measured by SRSI (secondary outcome), we will use a similar LMM as mentioned above. For electronic pill bottle data in the intervention group, we will also examine the trend of electronic pill bottom data over time with a GLMM which will include a first-order autoregressive (AR1) covariance structure, as described by Hedeker and Gibbons. We will also aggregate the electronic pill bottle data at different time points (0 and 3 months) and examine the association between the electronic pill bottle data and ART adherence data measured by SRSI using Spearman nonparametric correlation. Similar GLMMs or LMMs will be used for secondary outcomes, with GLMMs for binary outcomes and LMMs for continuous outcomes.

Aim 2. Conduct follow-up interviews to assess the barriers and facilitators to the recruitment, enrollment and retention procedures and to understand the acceptability of the intervention.

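### The planned sustainability test compares the end of the intervention with the time before it, on one follow-up viral load and with no margin, so no result can show sustainability

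*Combined protocol and SAP*

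**What the plan says.** In the Data Analysis section for Aim 1, after the primary model, the plan states: "A similar GLMM will be used to test sustainability of the intervention at month 3". The method is a non-inferiority test "to compare viral suppression rate between month 3 and baseline". It gives no margin. It does not say whether the time contrast is taken in the intervention arm or across both arms, or how a non-inferiority test fits the section's general rule of two-sided testing at 0.05.

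The timeline is set elsewhere:

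- Design Overview: CHAMPS Pilot "is a 3-month intervention guided by BA2C".
- Characteristics of the Population: "The total study duration will be 3 months".
- Procedures: both arms "will complete remote visits at the baseline and 3-month follow-up".
- Table 4: the row "Viral Load through dried blood spot kit" is marked under Screening and under 3 months, and nowhere else.
- Overview of Data Collection Time Points: "Follow-up visits will be scheduled 30 days before to 30 days after the target window".

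**The concern.** Sustainability means that an effect present when the intervention ends is still there some time later. Testing it takes an end-of-intervention value and a subsequent one. In this plan month 3 is the nominal end of the intervention, and the value it is compared with precedes the intervention. The test is therefore about change from before treatment, under a label that promises something else.

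Two consequences follow. First, either result can be misread: a pass as a lasting effect, a fail as an effect that wore off. Second, a change over time within participants does not separate the intervention from background improvement. The Study Purpose and Rationale and the Preliminary Data report that in the team's earlier community health worker trial both arms improved on several outcomes, including viral suppression, with no significant difference between them. The Sample Size section says this pilot is to estimate an effect size for future efficacy trials, so a mislabelled result could be carried into that planning.

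**Working it through.** **Step 1. The timeline.** The plan states no figure for this test, so there is none to reproduce. The structural check needs no assumptions.

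| Needed for sustainability | Present in the plan |
|---|---|
| Suppression at end of intervention | Yes, month 3 (within 30 days either side) |
| Suppression at a later time | No visit or viral load is planned after month 3 |
| Margin for acceptable loss | Not stated |

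Write p0, p3 and pL for the suppression rates before the intervention, at month 3 and at a later time. Sustainability concerns pL − p3. The planned test concerns p3 − p0. No value of p3 − p0 determines pL − p3. The 30-day window can move a participant's single month-3 sample before or after the end of the intervention, but it does not add a second sample.

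**Step 2. Overlap with the efficacy model.** The primary model already uses the same two time points and tests efficacy through the group-by-time interaction. The sustainability test has no data that this model lacks.

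**Step 3. How far the unstated choices move the result.** This is an illustration using a simple paired interval as a stand-in for the planned mixed model.

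Inputs from the plan: 40 participants, 1:1 allocation, 20% attrition. Completers: 20 × 0.8 = 16 in one arm, 40 × 0.8 = 32 in both.

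Assumed inputs: the entry suppression rate, the switching rates and the margin. Entry suppression is unknown. The Characteristics of the Population section describes participants as virally unsuppressed, but the eligibility criteria also admit people on a missed visit or on self-report ("or report either not virally suppressed in the past 12 months or virally unsuppressed in the past 12 months"). The second eligibility list, in the human subjects section, omits the missed-visit route but keeps the self-report one.

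True changes under the scenarios, with 30% of the unsuppressed gaining suppression and 10% of the suppressed losing it:

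- 0% at entry: 1.0 × 0.30 − 0 = +30 points
- 20% at entry: 0.8 × 0.30 − 0.2 × 0.10 = 0.24 − 0.02 = +22 points
- 40% at entry: 0.6 × 0.30 − 0.4 × 0.10 = 0.18 − 0.04 = +14 points
- 50% at entry with 20% switching each way: 0.5 × 0.20 − 0.5 × 0.20 = 0

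Interval: add 0.5 to each of the four paired cells. Let b = gains + 0.5, c = losses + 0.5 and N = n + 2. Then d = (b − c)/N, SE = √{[(b + c)/N − d²]/N}, and the test passes if d − 1.96 × SE > −margin. Pass probabilities are summed exactly over all possible counts of gains and losses.

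Probability of a pass, n = 16 / n = 32:

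| Entry rate, true change | 5-point margin | 10-point margin | 15-point margin |
|---|---|---|---|
| 0%, +30 | 90% / 100% | 99.7% / 100% | 100% / 100% |
| 20%, +22 | 64% / 93% | 84% / 99% | 91% / 99.8% |
| 40%, +14 | 36% / 67% | 61% / 88% | 72% / 96% |
| 50%, no net change | 5.5% / 10% | 18% / 27% | 26% / 47% |

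In the first three rows a pass is correct about change over time; the error would be to call it sustainability or an intervention effect. In the third row, with a true 14-point rise, the test at n = 16 and a 10-point margin still fails 39% of the time (100 − 61).

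**Step 4. Dependence on the interval method.** If nobody is suppressed at either time, then b = c = 0.5, d = 0 and SE = √(1/N²) = 1/N. The lower limit is −1.96/18 = −10.9 points at n = 16, which fails a 10-point margin, and −1.96/34 = −5.8 points at n = 32, which passes 10 and fails 5. Without the added 0.5 the interval has zero width at 0 and passes any positive margin. In the mixed model itself, the time effect cannot be estimated when nobody is suppressed at baseline. Elsewhere the constant matters less but still counts: in the no-net-change row at n = 16, dropping it moves 5.5% to 13.6% at 5 points and 26% to 35.7% at 15 points.

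**The case against.** The best defence is that this is a small matter, loosely worded. Sustainability is not in either aim, the Study Outcomes section or Table 4; the trial is a 40-person feasibility pilot; and the primary between-arm comparison is unaffected. All of that is true and limits the weight of the point. It does not make the test answer its question. That the result would mislead a later trial is a risk, not something the plan says will happen.

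A second line is that other data could fill the gap. Study Procedures and Materials lists viral load from electronic medical records among the data elements. However, no extraction after month 3 is planned, and the test names only month 3 and baseline.

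A third is that the arms are not wholly unspecified, since a similar mixed model analysed by intention to treat would contain both groups. That is fair. What is missing is which time contrast within that model is tested: one arm's or a pooled one.

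The figures in the working can also be challenged. They use a paired interval among completers instead of the planned model, rest on assumed rates and margins, and in the zero-suppression case depend on the 0.5 constant. This stands. They show sensitivity to unstated choices and are not predictions for this trial. The fault itself is one of design and label, and needs no calculation.

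**Conclusion.** The concern holds, and the text is wrong as written, not merely short of detail. Followed exactly, the plan would report on sustainability from a comparison that contains no planned measurement after the end of the intervention. That conclusion rests only on the plan's own timeline.

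The missing margin and unnamed contrast add to the problem. In the no-net-change illustration the chance of a pass runs from 5.5% to 47% across margins of 5 to 15 points and one arm or both. This range rests on an assumed 50% entry suppression, 20% switching each way and the adjusted paired interval.

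The point should be fixed, but it does not threaten the trial: it concerns a secondary analysis in a pilot, and the group-by-time efficacy comparison is untouched.

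**What to change.** Delete the two sentences on the sustainability and non-inferiority test and put in their place:

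> The pilot has a single post-baseline viral load, at about the end of the 3-month intervention, and does not assess sustainability. The change in the proportion with viral load ≤50 from the pre-intervention measurement to month 3 will be described within each arm with a 95% CI.

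The term pre-intervention measurement is deliberate: Table 4 places that viral load at Screening, and Eligibility Screening accepts a result up to 8 weeks old. Inference about the intervention stays with the between-arm comparison already planned.

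The cost is two sentences for two. No data, visits or models are added. The sponsor gives up a claim that the visit schedule cannot support. If sustainability is wanted, it would take a later viral load compared with month 3, with the margin, test level and contrast stated in advance; that is a larger change to the design and is not needed to correct the plan.
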